### **Study design**

The study will explore and assess the impact of “Refresh and Reconnect!”, on the health and well-being of persons with Mild Cognitive Impairment (MCI) or mild dementia - from here such individuals are referred to person(s) with cognitive impairment (PWCIs). “Refresh and Reconnect!” is a 6-week heritage-based intervention programme organised by the National Museum of Singapore (NMS), which includes guided gallery tours led by the museum’s Care Facilitator volunteers and artist-led hands-on activities based on various art forms.

The exploratory study adopts a quasi-experimental and mixed-methods design, incorporating *i) a quantitative component, and ii) a qualitative component*. The duration of each run of the “Refresh and Reconnect!” (R&R) programme is 6 weeks, and the data collection will take place over 4 programme rounds (Rounds 1 to 4), with 2 concurrent programme runs in each round, contributing to a total of 8 programme runs. For the period of study, participants enrolled into the R&R! programme will also be enrolled into the research study, with due informed consent. The study design for the first 2 rounds of the programme presented as below, and are repeated once more for a total of 8 programme runs:

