The pre-programme baseline assessment questionnaires will collect the following information for all PWCI-participants: socio-demographic, number of chronic diseases, stage of dementia (if applicable), status of activities of daily living (ADLs) and instrumental ADLs (IADLs), living arrangement. Both the pre-programme baseline assessment, as well as the post-programme assessment measure the following constructs:

- *Cognitive performance* (during screener; MoCA),
- *Health-related Quality of Life* (EQ-5D),
- *Quality of Life* (Control, Autonomy, Self-Realization, and Pleasure-11-SG; CASP-11-SG),
- *Anxiety & Depression* (Hospital Anxiety and Depression Scale; HADS),
- *Loneliness* (UCLA-LS-9 Loneliness scale),
- *Motivations to Learn* (Readiness-to-learn scale from Programme for the International Assessment of Adult Competencies (PIAAC))

In addition to the constructs measured above, PWCI will also be asked several open-ended questions relating to their experience of the programme, motivations to join the programme, as well as their previous experience with heritage-based or arts-based programmes. Responses from these questions, and engagement during the ethnographic observation will be used for selection of participants for the qualitative component and will also be analysed together with survey and in-depth interview responses; participants' responses from each research component will only be linked via the assigned unique participant ID.

After each session of the 6-week programme, participants will also answer a brief questionnaire [Labelled: "*ReCognition Programme Assessment PWCI*"] measuring their *Museum-based subjective well-being* (UCL Museum Wellbeing Measures toolkit). This measure will be administered in hard-copy paper, with each participant filling in one copy of the questionnaire at the end of the session (distributed either by NMS staff members of the research team). Each participant will either write their initials or first name on the

questionnaire for identification purposes - a member of the research team would subsequently key in these scores, pegged to respective participants' unique ID number. Subsequently once the scores are digitised and verified by another member of the research team, the hardcopy measurements will be shredded. This measure is expected to take **no more than 5 minutes** for participants to complete. Throughout the course of the study, participants would thus complete 6 instances of this questionnaire.

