#### **Ethnographic observations**

Ethnographic observations will be conducted by members of the study team throughout the R&R! programme run. Members of the study team will be on-site at the Reunion Space (within the National Museum of Singapore premise) throughout the course of **all R&R! programme runs** (n = 48 max visits) to conduct ethnographic observations. Members of the study team would stay for the approximately 2-hour duration of the R&R! session. The study team will remind programme facilitators or staff to inform participants of researchers' presence prior to the commencement of the programme as well.

During ethnographic observations, study team members will make observations about the conduct of the programme, PWCI's responses to programme components, interactions between PWCI's and Artists/Volunteers/Staff (including staff/volunteers from both the museum, and from relevant Active ageing centres or dementia day care centres), as well as how PWCI's interaction with the Reunion space.

Informal conversations will also be conducted with PWCI's, & volunteers present during the R&R! programme runs. Members of the study team will first briefly introduce themselves and the study prior to any conversations and seek the verbal consent of the participant; it will be emphasised that their participation is voluntary. Where possible, study team members will conduct conversations in participant's language(s) of choice.

As some PWCI-Participants will be accompanied by their caregivers or their migrant domestic workers (MDWs/helpers), the study team will also seek to obtain programme insights from this group in their capacity as a part of the PWCI's care system. Not all participants will have an accompanying family caregiver/MDW throughout the programme, as some caregivers may not be available or willing to accompany participants. Speaking to participants and caregivers may elucidate potential differences in the experiences for PWCI-participants with or without caregivers, and may help understand the role of caregivers' presence and involvement in the programme.

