## Please list people who will have access.

---

Findings from this study will be shared with staff from the National Museum of Singapore, as a fulfilment of the study requirements and as a deliverable for the project. Any research data provided for this purpose (e.g. Report, presentations) will only contain high-level de-identified, aggregated findings, or anonymised data. No raw interview transcripts and research data that could identify research participants will be accessible outside of the NUS research team. Interview responses will be aggregated for analysis and in presentations to any relevant stakeholders. Responses will be coded and presented in a cluster to maintain confidentiality and mitigate risk of exposure for research participants.

\*required

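### The museum's own staff may hand out the non-anonymous end-of-session well-being form, and the protocol does not say who collects it, although researchers are planned to be at every run

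*Protocol*

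**What the plan says.** Protocol, Component (i): Quantitative Study, introduces a short paper questionnaire on museum-based subjective well-being, completed at the end of each weekly session. It is "distributed either by NMS staff members of the research team". It is not anonymous: "Each participant will either write their initials or first name on the" form so that the scores can be matched to the study ID. Afterwards "a member of the research team would subsequently key in these scores", a second team member verifies them and the paper is shredded. Over a run, "participants would thus complete 6 instances of this questionnaire".

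Three other places bear on this:

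- **Ethnographic observations.** "Members of the study team will be on-site at the Reunion Space" for all runs, up to 48 visits, staying for the whole session of about 2 hours.
- **Access to Research Data** (list of people with access). NMS receives aggregated, de-identified or anonymised findings, and no "research data that could identify research participants will be accessible outside of the NUS research team".
- **Component (i), post-programme assessment.** This survey is conducted by trained research staff.

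**The concern.** NMS organises and hosts the programme, and the study's findings are a deliverable to it. A participant who has just spent two hours as the museum's guest may be handed a self-rating form by the museum's staff and asked to put initials or a first name on it. The natural risk is courtesy: answers kinder to the host than the participant would otherwise give, with an expected direction that favours the programme. If NMS staff distribute at some sessions and researchers at others, with no record of which, that influence cannot be examined afterwards.

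There is also a confidentiality side. The protocol assigns distribution and data entry but not the step between them. If NMS staff gather the completed sheets, they could see individual answers from people they can recognise.

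**Working it through.** No power, alpha or effect-size calculation applies. The check is a count and a comparison of sections.

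**1. Can researchers cover every session?** Study design gives "contributing to a total of 8 programme runs". R&R! Programme Design gives 6 weekly sessions per run, with the two concurrent runs meeting on different days.

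8 runs × 6 sessions = 48 sessions.

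This equals the maximum of 48 visits stated under Ethnographic observations. Planned researcher presence therefore reaches every session at which the form is used. Because 48 is a maximum, an occasional session without a researcher remains possible.

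**2. How many forms could be affected?** The quantitative sample is 64 to 120 participants, with 6 forms each.

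64 × 6 = 384; 120 × 6 = 720.

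This is a ceiling. It assumes that all forms are completed and that NMS staff hand out all of them. The number they would actually handle is not stated and could be zero.

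**3. Would the mark identify the person?** A run has 8 to 15 participants (Programme Recruitment & Quantitative Sampling), and NMS staff hold contact details of consenting participants (Access to Personal Data). In a group that small, initials or a first name will usually be enough for staff who know the group.

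**4. Who handles the form at each step?**

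| Step | Assigned to |
|---|---|
| Distribution | NMS staff or research team, on the natural reading of either |
| Completion | Participant |
| Collection | Not stated |
| Data entry | Research team |
| Verification | Another research team member |

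The gap is at collection. No section gives that step to NMS staff, and none keeps it from them.

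**5. Which results are exposed?** Component (i) lists the constructs measured both at baseline and post-programme, and the museum well-being measure is not among them. It is given only after sessions and has no pre-programme value. The linear mixed models described in the same component compare baseline with post-programme assessments. Any courtesy effect therefore sits in the session scores, not in that comparison.

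**The case against.** **The form is blank when handed out.** This is correct, and it defeats a stronger reading that a reader might infer: that Component (i) contradicts the data-access section. The text gives NMS staff at most the distribution of blank sheets and reserves data entry and verification for the research team. The access rule is left unprotected at one step; it is not contradicted.

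**NMS has no hold over these respondents.** A reader might infer pressure from the museum's discretion over places in later runs. Programme Recruitment & Quantitative Sampling gives that discretion for people who did not meet the eligibility criteria. They are not enrolled and never complete this form, so the argument is not available.

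**The quoted phrase is damaged.** A word or more seems to be missing, perhaps through text conversion, and the full sentence might limit the museum's role. That is possible. But either needs two alternatives, and NMS staff is the first one named. The source sentence should be checked.

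**The bias is unquantified and touches no described analysis.** Both parts are true. The protocol describes no analysis of the session scores and gives no figure for courtesy bias. This limits the weight of the point, but the scores are still collected as a measure of the programme.

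**Researchers at the session are already busy.** The engagement scale needs 10 minutes of observation per participant: 8 × 10 = 80 to 15 × 10 = 150 minutes, against a session of about 120, if one observer scores everyone in turn at each session. The number of observers and the frequency of scoring are not stated, so the workload is a fair caution. It does not defeat the change: the research team is already a named distributor, and the form takes no more than 5 minutes.

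**The setting stays the same.** Changing the distributor does not move the form out of the museum, where staff and volunteers assist participants. Some courtesy may remain. A closed return and a clear assurance still deal with who sees the answers.

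**Conclusion.** The point stands as an inexpensive improvement. The protocol lets staff of the evaluated organisation distribute an identifiable self-rating form immediately after the session, leaves collection unassigned, and gives no reason for doing so when researchers are planned to be present for all 48 sessions. By contrast, it gives the post-programme survey to research staff.

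Up to 384 to 720 session forms are exposed. The expected direction of bias is upward, which is a judgement, and its size is unknown. The conclusion rests on reading the broken phrase as naming NMS staff and the research team as alternatives, and on researchers attending as planned.

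It does not extend to the baseline to post-programme comparison, and it does not show a breach of the data-access rule.

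**What to change.** In Component (i), repair the distribution sentence and make three changes:

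1. Study team members distribute the form and collect it in a closed envelope or box.
2. Participants are told, before they fill it in, that museum staff, artists and volunteers will not see their answers.
3. At any session where no researcher is present, the person who handled the form is recorded, for example on the observation checklist.

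The cost is a few sentences of text, envelopes or a box, and about 5 minutes of a researcher's time at the end of each session. Over the whole study that is 48 × 5 = 240 minutes, or 4 hours. The team should confirm that this fits alongside the engagement-scale observations.

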### **Component (ii): Qualitative Study**

Utilising the Realist Evaluation Framework, the qualitative study utilises several phases of data collection methods to identify the contexts, mechanisms, and outcomes of the programme.

#### **Qualitative sampling**

During the informed consent process, participants will also be informed of the ethnographic observations, as the researchers' presence throughout the programme. Participants will be informed of the possibility of their being selected for the in-depth interviews.

A total of 16 PWCI will be identified to participate in the in-depth interviews, based on their quantitative baseline assessment and responses to the survey, open-ended questions and engagement during the ethnographic observations. For the purposes of the qualitative portion of the study, participants will be identified using the unique participant ID previously assigned during the quantitative component.

As multiple instances of the programme may run simultaneously, participants will be sampled across different runs/iterations of the programme. 4 PWCI-participants will be sampled from each concurrent run of the programme (i.e. 4 participants for the first consecutive two runs, 4 from the next two consecutive runs, etc.) for a total of 16 participants. Sampling participants across different runs of the programmes not only enable the research team to attain a more diverse sample of older persons but also serves to understand how variations in the programme affect participants' experiences. A diverse sample of participants across gender, ethnicity and socio-economic status will be obtained as much as possible.

Non-PWCI participants, such as museum staff and artists, will be invited to participate in the study and follow consent-taking processes. Ethnographic interviews, referring to informal and unstructured interviews that occur during ethnographic observations or programme sessions will be conducted with non-PWCI participants such as: Museum staff (max. n=3) organizing the sessions, and programme artists facilitating the sessions (max. n= 6). Programme volunteers assisting PWCI during the sessions will be engaged in casual conversations as part of the ethnographic observation component.

#### **Ethnographic observations**

Ethnographic observations will be conducted by members of the study team throughout the R&R! programme run. Members of the study team will be on-site at the Reunion Space (within the National Museum of Singapore premise) throughout the course of **all R&R! programme runs** (n = 48 max visits) to conduct ethnographic observations. Members of the study team would stay for the approximately 2-hour duration of the R&R! session. The study team will remind programme facilitators or staff to inform participants of researchers' presence prior to the commencement of the programme as well.

During ethnographic observations, study team members will make observations about the conduct of the programme, PWCI's responses to programme components, interactions between PWCI's and Artists/Volunteers/Staff (including staff/volunteers from both the museum, and from relevant Active ageing centres or dementia day care centres), as well as how PWCI's interaction with the Reunion space.

Informal conversations will also be conducted with PWCI's, & volunteers present during the R&R! programme runs. Members of the study team will first briefly introduce themselves and the study prior to any conversations and seek the verbal consent of the participant; it will be emphasised that their participation is voluntary. Where possible, study team members will conduct conversations in participant's language(s) of choice.

As some PWCI-Participants will be accompanied by their caregivers or their migrant domestic workers (MDWs/helpers), the study team will also seek to obtain programme insights from this group in their capacity as a part of the PWCI's care system. Not all participants will have an accompanying family caregiver/MDW throughout the programme, as some caregivers may not be available or willing to accompany participants. Speaking to participants and caregivers may elucidate potential differences in the experiences for PWCI-participants with or without caregivers, and may help understand the role of caregivers' presence and involvement in the programme.

Members of the study team may also have informal conversations with NMS staff, programme volunteers, as well as the artist-facilitators involved in the R&R! programme, in order to better understand their experience conducting, assisting, and organising the programme. The study team will note these observations for further discussion in ethnographic unstructured interviews with artists and NMS staff; programme volunteers will not be involved in these subsequent ethnographic unstructured interviews, and will only be engaged in casual/informal conversations throughout the study. The study team will be sensitive to the needs of artists and staff and will ensure that observations and informal conversations do not interfere with the smooth operations and the experience of the programme. Members of the study team will also emphasise the voluntary nature of these conversations.

The study team will also identify participants for in-depth interviews; **4 PWCI-participants** from each **concurrent run** of the programme (total n=16). This recruitment will take place on-site during a session of the R&R! programme. Should a selected participant be willing to take part in the in-depth interviews, study team members will seek verbal consent to provide a follow-up call to the participant to arrange for interview after the conclusion of that specific run of the R&R! programme. Participants will be reminded that their participation in the in-depth interviews are voluntary, and that participation or non-participation will not impair their ability to complete the R&R! programme nor the post programme assessment in the quantitative component of the study.

These informal conversations are conducted to gain understanding of the key elements which drive the R&R programme and their ensuing impact on PWCI's lives. As conversations may vary highly between different persons, and at different points in the R&R! programme, no 'interview guide' is provided. As part of the ethnographic observations however, members of the study team will also utilise the Engagement of a Person with Dementia Scale, an observational scale which requires that members of the research team observe each PWCI-participant for a duration of 10 minutes and score them across different domains. These scores are recorded in the ethnographic observation checklist (attached, with each participant identified only by their unique participant ID number).

Informal chats or unstructured interviews will not be audio-recorded. Photographs and videos may be taken

with consent, strictly to supplement note-taking processes; where participants or staff members did not give consent for photography or videography but happen to be captured in any photograph or video, the study team will mask faces or any identifiable features (E.g. blurring, mosaic). No personal data of participants will be recorded as part of the note-taking process for ethnographic observations except for participants who are identified for and are agreeable to participate in the IDIs. Any notes taken as part of the ethnographic observations will be analysed in tandem with findings in other study components.

### **Ethnographic Unstructured Interviews with service provider (Museum organising staff)**

The team will carry out informal and unstructured interviews with NMS staff (max. n=3) which will be divided into two sections: Pre (Pi) and Post (Pii)-programme and carried out accordingly – at the start (or early into study period) and at the end of the programme.

In P(i), questions are asked to document NMS staff's processes, motivations and objectives of designing museum-based interventions for PWCIIs, including outreach efforts, programme expectations and perceptions of 'success'. In P(ii), questions pertaining to feedback about each session, including the curation and experience of working with different artists-facilitators, as well as programme enablers and barriers that contribute to or hinder a successful run, will be asked.

As each NMS staff's role in operationalising and conducting the R&R! programme is unique, and each conversation will focus on the specific challenges and experiences relating to this role, no 'interview guide' provided. Study team members will rely on fieldnotes from ethnographic observations (which include casual conversations with NMS staff) to guide the interviews further, in addition to the themes highlighted above.

Conversations with NMS staff may be audio-recorded and subsequently transcribed, with consent from NMS staff, for analytical purposes. Should NMS staff decline audio-recording, members of the study team will continue to take detailed notes of the session. Each NMS staff interviewed will be assigned a unique participant ID, and all identifiable information will be anonymised or removed from any research data at the earliest time possible. Audio-recordings from these interviews will be identified only by the unique participant ID.

### **Ethnographic Unstructured Interviews with service provider (Artists)**

Each programme run may involve different artists facilitating a few sessions. Each artist (max. n=6) will be interviewed separately by the research team. To minimize research fatigue/ burden on artists, short, unstructured interviews will be conducted with artists throughout the overall programme segment.

Unstructured interviews will focus on their programme vision and previous exposure with curating programmes for older persons and experiences facilitating the sessions. They will also be asked to evaluate their own strengths and weaknesses as facilitators, their expectations of the programme, and how their own experience conducting the programme matches their expectations (or not), as well as other sources of enablers and barriers that can promote or hinder the success of their program segment.

Conversations with artists may be audio-recorded and subsequently transcribed, with consent from the artists, for analytical purposes. Should artists decline audio-recording, members of the study team will continue to take detailed notes of the session. Each artist interviewed will be assigned a unique participant ID, and all identifiable information will be anonymised or removed from any research data at the earliest time possible. Audio-recordings from these interviews will be identified only by the unique participant ID.

